5.4 Safety

All AEs, clinical laboratory results, physical examinations, vital signs, and 12-lead ECG readings data will be evaluated for safety. The data from safety population defined in [Section 5.1](#) will be used for safety analysis. Statistical analyses will be [REDACTED] and descriptive in nature.

5.4.1 Adverse Events

AEs will be coded using MedDRA version of 19.1 or later. Only treatment-emergent AEs will be analyzed. A treatment-emergent AE is defined as any AE that has an *onset* date and time that is *on or after* the date of the first dose of study treatment, or that has *worsened after* the date of the first dose of study treatment. In the case of a worsening AE, the AE is supposed to be recorded as a new event with an onset date after first dose of study drug. Therefore, all treatment emergent AEs will be captured as AEs that have an onset date that is on or after date of first dose of study drug.

If an AE had a missing onset date and a missing resolution date, or had a missing onset date and a resolution date which was after the first day the subject was on study drug, or an onset date which was after the date of the first day the subject was on study drug, the event is considered treatment emergent. If the onset date of the AE was the same as date of the first day the subject took study drug the event is considered treatment-emergent. When partial AE start or end date exists, before determining whether treatment-emergent or not, the following imputation rules are applied.

Partial start dates:

If day is missing (only month and year are present)

- If year and month are same as treatment start date then assign the day of treatment start date to the partial date
- Otherwise assign the day to '01'

If only year is present

- If year is same as treatment start date then assign the month and day of the treatment start date to the partial date
- Otherwise assign the month and day to 'January-01'

Partial end dates:

If day is missing (only month and year are present)

- If year and month are same as the year and month of study end date then assign the day of the study end date to the partial date
- If year and month are prior to the year and month of study end date then assign the last day of the month (28, 29, 30 or 31)

If only year is present

CONFIDENTIAL

The information contained herein may not be used, disclosed, or published without the written consent of Biogen Idec MA Inc.

	Protocol 109MS310 An Open-Label Study to Assess the Effects of BG00012 on Lymphocyte Subsets in Subjects With RRMS	Final Version 1.0
---	---	--------------------------

- If year is same as the year of study end date then assign the month and day of the study end date to the partial date
- If year is prior to the year of study end date then assign ‘December-31’ to the partial date.

If the study is ongoing and study end date is not available then the cut-off date will be used in the place of study end date

AE overview

The summary of treatment-emergent AEs will include the number of subjects and percentage for the following categories: at least one treatment-emergent AE, at least one moderate or severe treatment-emergent AE, at least one severe treatment-emergent AE, at least one related treatment-emergent AE, at least one treatment-emergent SAE, discontinuing treatment due to an event and withdrawing from study due to an event. A listing of all AEs will be presented for all subjects.

AEs

- The incidence of treatment-emergent AEs classified by the appropriate system organ class (SOC) and preferred term (PT) will be summarized.
- The incidence of treatment-emergent AEs classified by PT will be summarized.
- The incidence of treatment-emergent AEs considered as related to study drug classified by the appropriate SOC and PT will be summarized. Treatment-related is defined as events with a “possibly” or “related” relationship to study drug.
- Incidence of treatment-emergent AEs by relationship to study drug will be summarized. In the relationship to study drug column within each SOC and PT, a subject was counted only once and only in the category of strongest relationship to study drug.
- Incidence of treatment-emergent AEs by severity will be summarized. If a patient experiences an event more than once with varying severity during a study phase, he/she will be counted only once with the maximum severity within each SOC and PT.
- The incidence of treatment-emergent AEs that led to the discontinuation of study drug will be presented by SOC and PT. A listing of these AEs will also be presented.
- The incidence of treatment-emergent AEs that led to premature withdrawal from the study will be presented by SOC and PT. A listing of these AEs will also be presented.
- The incidence of treatment-emergent AEs that led to temporary dose interruption will be presented by SOC and PT.

CONFIDENTIAL

The information contained herein may not be used, disclosed, or published without the written consent of Biogen Idec MA Inc.

	Protocol 109MS310 An Open-Label Study to Assess the Effects of BG00012 on Lymphocyte Subsets in Subjects With RRMS	Final Version 1.0
---	---	--------------------------

- The incidence of treatment-emergent AEs that led to dose reduction will be presented by SOC and PT.

SAEs and severe AEs

- The incidence of treatment-emergent SAEs will be presented by SOC and PT. Individual SAEs will be listed. The information presented will include subject ID, treatment, SOC and PT, date of onset, severity, and relationship to and action taken with the study drug.
- The incidence of treatment-emergent severe AEs classified by SOC and PT will be summarized.

Infections

The incidence of treatment-emergent infections, serious infections, and potential opportunistic infections by system organ class and preferred term will be summarized by subgroups based on the ALC values over time.

PML

Given that PML has been observed very rarely in patients who receive BG00012, any PML cases in this study will be listed.

Pancreatitis

Listing of events associated to pancreatitis will be presented.

Death

Death is classified as an outcome, not as an AE. Therefore, cause of death will be listed as the AE. Death will only be listed as an AE when the cause of death is unknown (e.g., in the case of sudden death). . The information presented will include subject ID, treatment group, SOC and PT, date of death, cause of death, and relationship to the study drug.

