DMF was generally well tolerated and demonstrated an acceptable safety profile. The most common AEs associated with DMF were flushing and gastrointestinal (GI) events. In subjects who experienced these types of events, the events were generally mild or moderate in intensity, tended to decrease in incidence after the first month, and only infrequently led to treatment discontinuation. There are a number of potential management strategies for these side effects. In the Phase 2 and 3 controlled and uncontrolled clinical studies in subjects with RRMS, BG00012 treatment was associated with a gradual decrease from baseline in mean leukocyte counts driven primarily by decreases in mean lymphocyte counts; mean lymphocyte counts decreased by approximately 30% of their baseline value after 1 year and then plateaued and remained stable through more than 6 years of follow-up. While decreases in lymphocyte counts have been observed with BG00012 treatment, in the placebo controlled Phase 2 and 3 studies BG00012 was not associated with an increased risk of infection, serious infection, or opportunistic infection compared with placebo. However, in the long-term extension study (109MS303), progressive multifocal leukoencephalopathy (PML) has occurred in the setting of severe, prolonged lymphopenia following BG00012 administration. PML has also been reported in the postmarketing setting in the presence of prolonged moderate to severe lymphopenia. The majority of all cases occurred in patients with lymphocyte counts $<0.5 \times 10^9/L$. With open-label

CONFIDENTIAL

The information contained herein may not be used, disclosed, or published without the written consent of
Biogen MA Inc.

and marketed use of BG00012, there has been no other evidence of an increased risk of infections, serious infections, or opportunistic infections.

See the Investigator's Brochure for detailed information on clinical studies.

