5.3.1 Analysis of the Primary Endpoint

The primary endpoints are the changes in lymphocyte subset counts for up to 48 weeks. The actual value, change and percent change from baseline in count and percent for each lymphocyte subset will be descriptively summarized at each applicable visit. Graphical display of median (Q1-25 percentile/Q3-75 percentile) of actual value and percent change from baseline in count and percent for each lymphocyte subset over time will also be presented. The Wilcoxon signed rank test will be used to test if the change and percent change from baseline in count and percent for each lymphocyte subset is different from zero. Listings of lymphocyte subsets will also be presented.

Furthermore, the primary endpoints will be summarized in various ALC subgroups to evaluate the nature of change in each subset in relation to the change in ALC.

ALC subgroups of interest include (1) subjects who have all ALC values \geq LLN ($0.91 \times 10^9/L$) up to Week 48, and (2) subjects who have at least 1 ALC value $<$ LLN over 48 weeks. A mixed model for repeated measures (MMRM) will be used to estimate the difference between ALC subgroups at each post-baseline visit up to Week 48. The model will be fitted with the change from baseline in count up to Week 48 for each of the TBNK lymphocyte subset as the dependent variable and will include ALC subgroup (all ALC values

CONFIDENTIAL

The information contained herein may not be used, disclosed, or published without the written consent of Biogen Idec MA Inc.

	Protocol 109MS310 An Open-Label Study to Assess the Effects of BG00012 on Lymphocyte Subsets in Subjects With RRMS	Final Version 1.0
---	---	--------------------------

\geq LLN up to Week 48; at least 1 ALC value $<$ LLN over 48 weeks), visit, corresponding Baseline counts, age, gender, and ALC subgroup-by-visit interaction as fixed effects. An unstructured variance-covariance matrix structure will be used in the MMRM model. Least squares (LS) mean, standard error, LS mean difference, 2-sided 95% confidence intervals (CIs) and p-values will be reported. Before the MMRM analysis, appropriate transformation may be performed based on the distribution of each TBNK lymphocyte subset parameter. The same analysis may be applied to other subsets.

Additional subgroups based on ALC values over time are defined:

- 1) ALC $< 0.5 \times 10^9/L$ for ≥ 6 months (24 weeks);

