- 2) $0.5 \times 10^9/L \leq ALC < 0.8 \times 10^9/L$ for ≥ 6 months (excluding $< 0.5 \times 10^9/L$ for ≥ 6 months);
- 3) $<$ LLN any time (excluding $< 0.8 \times 10^9/L$ for ≥ 6 months);
- 4) ALC always \geq LLN.

Summary of actual value, change and percent change from baseline in count and percent for each lymphocyte subset will be presented by the ALC subgroups defined above.

The following subgroups analyses based on ALC during the first 48 weeks will be performed:

- 1) At least 2 ALC values $<$ LLN in the first 48 weeks;
- 2) Always \geq LLN or with one ALC $<$ LLN in the first 48 weeks

Additionally subgroups analyses based on baseline ALC quartiles will also be explored. The same descriptive summary on these subgroups will be applied to the count and percent for the TBNK lymphocyte subsets and may be applied to other subsets. Additional subgroups of interest may also be explored.

The correlation between TBNK actual value and ALC will be summarized by visit and also presented as plots.

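### Infections are planned as crude percentages by ALC groups fixed over the whole study, so the comparison can be biased in either direction; a rate table by current ALC state is needed beside it.

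*SAP*

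**What the plan says.** SAP 5.4.1, under Infections, plans one tabulation of incidence for all treatment-emergent infections, the serious ones and the possibly opportunistic ones. Its sentence ends: "potential opportunistic infections by system organ class and preferred term will be summarized by subgroups based on the ALC values over time". It does not say which subgroups these are.

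The nearest definition is in SAP 5.3.1, introduced by "Additional subgroups based on ALC values over time are defined". It gives four groups (counts in 10^9/L):
- below 0.5 for at least 24 weeks;
- 0.5 to below 0.8 for at least 6 months;
- below LLN at any time, outside the prolonged categories;
- always at or above LLN (0.91).

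None has a week limit. The pair that follows does: "The following subgroups analyses based on ALC during the first 48 weeks will be performed".

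Incidence elsewhere in SAP 5.4.1 means subjects with an event: "The summary of treatment-emergent AEs will include the number of subjects and percentage". Protocol 16.4.2.1 likewise speaks of subject incidences. To count, an event need only start on or after first dose. SAP 5.2.5 summarizes time on study, but neither by ALC group nor as a denominator for infections.

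**The concern.** The groups are fixed labels assigned from counts that come later, and two faults follow.

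1. A subject whose ALC first falls at Week 72 carries the low label from Day 1. Infections in the first 72 weeks, with a normal ALC, are tabulated as infections in a lymphopenic subject. This dilutes a real association.
2. To enter a prolonged-low group, a subject must remain under observation through at least 24 weeks of low counts. A subject who leaves at Week 6 with normal counts goes to the always-normal group with little time at risk. Crude percentages ignore the difference, so an association can appear where none exists.

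The question matters for this drug. Protocol 5.3.2 states that "PML has also been reported in the postmarketing setting in the presence of prolonged moderate to severe lymphopenia" and that most PML cases had counts below 0.5 × 10^9/L. This table is the SAP's only stated summary relating infections to lymphocyte count.

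**Working it through.** **Inputs from the documents.** AEs are recorded from first dose to the final Follow-Up Visit (Protocol 15.3.1), which is Week 100 (Protocol 7.2.3). Sample size (SAP section 4): 180 evaluable at Week 48, and 180 / 0.90 = 200 enrolled, so the plan expects 10% loss by Week 48. Expected group sizes to Week 48: 0.24 × 180 = 43 with at least one value below LLN, and 0.16 × 180 = 29 with at least two.

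**No plan figure to reproduce.** The documents give no infection rate, effect of low ALC on infection, or onset-time distribution. These are assumed below.

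**Fault 1, dilution.** Assume Poisson infections at r = 0.5/52 per week, T = 100 weeks, and a rate of 2r once ALC is low. For onset at week s:
- whole-study-group rate ratio = [s + 2(100 − s)] / 100;
- risk = 1 − exp(−r[s + 2(100 − s)]);
- reference risk, never low = 1 − exp(−0.962) = 0.618.

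| Onset | Rate ratio | Risk if low | Risk ratio |
|---|---|---|---|
| Day 1 (no misattribution) | 200/100 = 2.00 | 0.854 | 1.38 |
| Week 24 | 176/100 = 1.76 | 0.816 | 1.32 |
| Week 48 | 152/100 = 1.52 | 0.768 | 1.24 |
| Week 72 | 128/100 = 1.28 | 0.708 | 1.15 |

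Compare within a column. For onset at Week 48, misattribution takes the rate ratio from 2.00 to 1.52 and the risk ratio from 1.38 to 1.24. The step from 2.00 to 1.38 is only the ceiling on percentages at this infection rate.

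**Fault 2, unequal time at risk, no true link.** Take a constant loss hazard h = −ln(0.90)/48 = 0.00219 per week. With infection rate r, the chance of no infection over t weeks of possible follow-up is E(t) = [h/(h + r)][1 − exp(−(h + r)t)] + exp(−(h + r)t).
- All subjects: 1 − E(100) = 0.564.
- Subjects who must reach Week 28 (first post-baseline count at Week 4, plus 24 weeks): 1 − exp(−28r) × E(72) = 0.592.
- Ratio 0.592 / 0.564 = 1.05 with no effect of ALC. The always-normal group would do worse than all subjects, because early leavers collect there.

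**Both faults together.** A simulation compared one ever-low group with always-normal. It assumed 0.1, 0.5 or 1.0 infections per year, 30% of subjects susceptible to a low ALC, first detection at a scheduled visit (early-weighted, uniform or late-weighted), and 0%, 10% or 30% loss by Week 48 continuing at the same hazard.

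| Quantity | No true link | True rate ratio 2 |
|---|---|---|
| Low group's infections that precede the first low ALC | 31–58% | 18–41% |
| Crude risk ratio, no loss | 0.99–1.02 | 1.09–1.57 |
| Crude risk ratio, 10% loss | 1.05–1.12 | 1.18–1.70 |
| Crude risk ratio, 30% loss | 1.17–1.36 | 1.35–1.90 |
| Rate ratio, whole-study groups | 0.99–1.02 | 1.42–1.70 |
| Rate ratio, split at first low ALC | 0.99–1.02 | 1.99–2.04 |

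At 10% loss, mean follow-up was 94–97 weeks in the low group and 87–88 weeks in the always-normal group. Dividing by person-time removes the false link but not the dilution. Splitting events and time by ALC state removes both.

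**The case against.** A reader might infer that the table hides any link between low ALC and infection. The documents and the arithmetic do not support that. The two faults pull in opposite directions, and a true rate ratio of 2 stayed above 1 in every scenario run. Nor is it fair to set the table's 1.24 against 2.0, because one is a ratio of percentages and the other a ratio of rates.

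Other points stand in part:
- **The subgroup link is inferred.** SAP 5.4.1 does not cite 5.3.1. The near-identical wording and the missing week limit make the whole-study reading the natural one, but the SAP should say so.
- **Timing can be checked by case.** All AEs are listed, SAEs with onset date, as are PML cases (SAP 5.4.1), haematology by subject (5.4.2) and AEs in the lymphocyte follow-up period (5.4.6). This lets a reader place a serious infection against the ALC. It gives no rate or denominator by ALC state.
- **The analysis is descriptive.** Safety is not a primary or secondary objective, and no test or error rate attaches to infections. A descriptive table can still mislead.
- **The false-link figure is modest at the planned loss.** The 1.17–1.36 range needs 30% loss by Week 48, three times what the plan allows for.
- **Numbers are small.** About 29 of 180 subjects were expected to have even two values below LLN by Week 48, so any split will be imprecise.

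**Conclusion.** The concern holds as a two-way bias in a descriptive safety table. Followed as written, the plan counts infections before the ALC fall as infections in low-ALC subjects and takes no account of time at risk. Under the assumptions shown, a doubling of the rate from Week 48 appears as a rate ratio of 1.52 if the whole-study groups are kept; with no true link, the plan's 10% loss gives a crude risk ratio of about 1.05 to 1.12. The infection rate, effect, onset times and loss pattern are all assumed, so these figures show direction and plausible range and do not predict this trial's results. The conclusion also assumes that the infection subgroups are those of SAP 5.3.1. No primary or secondary endpoint is affected. The change should be made, because the table addresses a question the protocol's own background raises.

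**What to change.** 1. Keep the planned table and cite SAP 5.3.1 for its subgroups.
2. Add one descriptive table of infections and serious infections per person-year by ALC state at the time, using the last ALC before onset: at or above LLN, 0.8 to below LLN, 0.5 to below 0.8, and below 0.5 (× 10^9/L). Split each subject's events and person-time across states, so that infections before the first low value go to the state at or above LLN.
3. If numbers allow, repeat by cumulative time to date below 0.5 and below 0.8. Where cells are sparse, present totals rather than SOC and PT.

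The cost is one extra table from AE onset dates and serial ALCs already collected. The SAP should state its limits. ALC is carried forward between counts, which are 4 weeks apart to Week 12 and at least every 4 weeks for a confirmed count below 500/mm³, but otherwise 12 weeks apart. Estimates will be imprecise. Low-ALC time is confounded with later study time, because counts fall gradually over the first year (Protocol 5.3.2), and partly with time off drug, because persistent low counts lead to withholding (Protocol 11.3.1).

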5.4.2 Clinical Laboratory Results

The following laboratory parameters will be analyzed:

- Hematology: WBC, lymphocytes, neutrophils, monocytes, eosinophils, basophils, RBC, hemoglobin, hematocrit, platelets.
- Blood chemistry: ALT/SGPT, AST/SGOT, alkaline phosphatase (ALP), total bilirubin, BUN/urea, creatinine, sodium, potassium, chloride, bicarbonate, calcium, magnesium, phosphorus, glucose, uric acid.

Shift analyses

Laboratory data will be summarized using shift tables. Each subject's hematology and blood chemistry values will be flagged as "low", "normal", or "high" relative to the normal ranges of the central laboratory or as "unknown" if no result is available. Shifts from baseline to

CONFIDENTIAL

The information contained herein may not be used, disclosed, or published without the written consent of Biogen Idec MA Inc.

high/low status for hematology and blood chemistry parameters will be presented. Subjects need to have at least one-post baseline evaluation in order to be included in the analysis. In addition, the shift from baseline to the maximum post-baseline value will be presented for selected blood chemistry parameters (ALT, AST, alkaline phosphatase and total bilirubin). The rationale for using the maximum values or worst values is that should a treatment affect a laboratory value, that value could be affected at different times for different subjects. Therefore, the analyses present the most extreme values for each subject over time.

In addition, summary of maximum post-baseline values for selected blood chemistry parameters (ALT, AST, and total bilirubin) will be presented. For liver function tests ALT, AST, the number and percentage of subjects with post-baseline values classified by categories will be summarized. The categories are defined as: $\leq 1 \times \text{ULN}$, $> 1 \times \text{ULN}$, $\geq 3 \times \text{ULN}$, $> 5 \times \text{ULN}$, $> 10 \times \text{ULN}$, and $> 20 \times \text{ULN}$, where ULN is the Upper Limit of the Normal value. For total bilirubin, the categories are: $\leq 1 \times \text{ULN}$, $> 1 \times \text{ULN}$, $\geq 1.5 \times \text{ULN}$, and $> 2.0 \times \text{ULN}$. A graphical summary of baseline and worst post-baseline values for selected laboratory parameters (WBC and lymphocyte) will also be presented.

Change from baseline analyses

Summary of hematology and blood chemistry values and change from Baseline by visit up to Week 96 will be presented. Graphical display of mean (+/- SE) of change from Baseline for hematology and blood chemistry parameters over time will be presented. Subject listings of hematology and blood chemistry will also be presented.

Abnormality analyses

Additional summary statistics will be presented for potentially clinically significant abnormalities for selected laboratory parameters. For example, the worst post-baseline values for WBC, lymphocyte, platelet, RBC, neutrophils, hemoglobin, classified based on clinically meaningful cut-off values, will be summarized.

Table 4: Definition for potentially clinically significant abnormalities for selected laboratory parameters

Parameter (unit)	Definition of potentially clinically significant abnormalities (each defined separately)
WBC ($\times 10^9/\text{L}$)	< 3.0 ≥ 16
Lymphocyte ($\times 10^9/\text{L}$)	< 0.8 < 0.5 > 12
Neutrophil ($\times 10^9/\text{L}$)	≤ 1.0

CONFIDENTIAL

The information contained herein may not be used, disclosed, or published without the written consent of Biogen Idec MA Inc.

	<1.5 >=12
RBC (x 10 ¹² /L)	<=3.3 >=6.8
Hemoglobin (g/L)	<=100
Platelet count (x 10 ⁹ /L)	<=100 >=600

